23.0 Provisions to Protect the Privacy Interests of Participants*

23.1 The study team will take great care to protect participant privacy.

Recruitment and enrollment will occur privately.

Participants will be assigned a study number. Surveys will be completed confidentially and will not contain identifying information. We will use a unique, participant-created code to link study surveys over time, such that participant identity is not linked to the study survey data.³⁹ Contact information used to facilitate follow-up survey completion will be stored in a separate REDCap tool and thus not linked to study data. Identifying information necessary for gift card provision will be obtained upon survey completion via a separate REDCap tool and thus this information will not be linked to an individual participant's survey data.

All data will be managed in accordance with the CM Institutional Review Board and HIPAA requirements to ensure confidentiality and protection of research participants. Study team members will not use study data and records for any purpose other than for conducting the study. PHI will be kept in a password protected database that is separate from the study survey database. PHI will be deleted at the earliest opportunity. There are no patient identifiers recorded in the permanent research record. Clinical information will not be released without written permission of the participant, except as necessary for monitoring by IRB, the FDA, the OHRP, the Sponsor, or the Sponsor's designee.

23.2 To ensure participants feel at ease with study procedures, we will thoroughly explain study procedures, ensure ample opportunity for questions at any point during the study, provide assurance that participation is voluntary and can be terminated at any point, and provide assurance that the decision to participate or not will not impact the participant's relationship with Children's Mercy

23.3 Study team members will only have access to data required to complete their designated study duties. Study team member training will include necessity of and mechanisms to protect privacy and confidentiality.

24.0 Withdrawal of Participants*

All participants may withdraw from the study at any time by notifying the research team. If a participant withdraws from the study, any data collected up to that point will be kept and deidentified for analysis purposes.

DATA MANAGEMENT

25.0 Data Collection*

Sources of data include adolescent participants (surveys, audio recordings of ED-HEART delivery), the medical records of adolescent participants (chart review by study team), the Cerner ED tracking board, and Health Educator field notes. See Section 9 (Surveys and Psychometric Testing) for a detailed description of survey data. **Sensitive Data:** Study data includes report of ARA and receipt of POC RSH resources accessed during the ED visit.

Identifiable Data: PHI sufficient to enable delivery of the study follow-up survey and to enable monitoring of intervention fidelity (i.e., audio recording of ED-HEART delivery) will be recorded. This information will not be retained as a part of permanent study data.

| | | |
|------------------|----------------------------------------|----------------------------------------------|
| 1. Name/Initials |  Accessed only |  Recorded |
|------------------|----------------------------------------|----------------------------------------------|

| | | |
|-------------------------------------------------------------------------------------------------------------------------------------------------------------------------------|----------------------------------------|----------------------------------------------|
| 2. All elements of date (except year) directly related to an individual (e.g., date of birth, admission date, discharge date, date of death) |  Accessed only |  Recorded |
| 3. Medical record number |  Accessed only |  Recorded |
| 4. Account number |  Accessed only |  Recorded |
| 5. Health plan identification number |  Accessed only |  Recorded |
| 6. Social Security Number |  Accessed only |  Recorded |
| 7. Device identifiers and serial number |  Accessed only |  Recorded |
| 8. Certificate/License number |  Accessed only |  Recorded |
| 9. Telephone number |  Accessed only |  Recorded |
| 10. Fax number |  Accessed only |  Recorded |
| 11. Email addresses |  Accessed only |  Recorded |
| 12. Web addresses (URLs); Internet IP addresses |  Accessed only |  Recorded |
| 13. Street address, city, county, precinct, zip code or equivalent geographical codes |  Accessed only |  Recorded |
| 14. Full face photographic images and any comparable images |  Accessed only |  Recorded |
| 15. Biometric identifiers, including finger and voice print |  Accessed only |  Recorded |
| 16. Vehicle identifiers and serial numbers, including license plate number |  Accessed only |  Recorded |
| 17. Any other unique identifying number, characteristic or code that may help identify individual participants including their initials (e.g., student or employee ID number) |  Accessed only |  Recorded |
| 18. Elements of date, including year, for persons 90 years or older |  Accessed only |  Recorded |
| 19. Other: |  Accessed only |  Recorded |

26.0 Adverse Events and Unanticipated Problems*

Monitoring: The PI and study team will meet weekly during enrollment and the 3-month follow-up period to identify and discuss adverse events and unanticipated problems. Study team members will promptly notify the PI if an adverse event or unanticipated problem is identified.

Reporting: We will follow Policy 5.11 Reportable Events of the CM Research Program Policies and Procedures in regards to reporting adverse events and other unanticipated problems to the CM IRB.

27.0 Data Analysis

We will generate a descriptive summary of feasibility using the Bowen model's eight constructs (Table 2).

| Table 2: Assessment of Bowen Feasibility Constructs | | |
|-----------------------------------------------------|-------------------------------------------------------------------------|-----------------------------------------------------------------------------------------------------------------------|
| Construct | Definition | Assessment measures |
| Acceptability | To what extent is ED-HEART suitable? | Adolescent surveys, Health Educator field notes |
| Demand | To what extent is ED-HEART likely to be used? | Proportion of screened adolescents eligible; proportion of eligible adolescents enrolled; Health Educator field notes |
| Implementation | To what extent can ED-HEART be delivered as planned? | Fidelity assessment per adolescent survey, Health Educator field notes, audio recordings of intervention delivery |
| Practicality | What factors make delivery challenging or facilitate delivery? | Health Educator field notes |
| Adaptation | To what extent does ED-HEART perform in a new system? | Comparison with published outcomes in original setting ³³ |
| Integration | To what extent can ED-HEART be integrated within existing system? | Health Educator field notes |
| Expansion | To what extent can the existing system be expanded to provide ED-HEART? | Health Educator field notes |
| Limited efficacy | Are ED-HEART outcomes promising? | Primary outcome: any ARA at 3-month follow up ³³ , per adolescent survey |

Acceptability ratings will be collapsed to dichotomous variables. ED-HEART will be deemed acceptable if the test of the proportion of very/fairly satisfactory ratings for adolescents, the health educator, and ED staff being <85% is not statistically significant. We will compare ED length of stay between the two arms, and calculate the mean/median number of interruptions per participant, with a list of reasons for interruption. For limited efficacy assessment, our primary outcome is any ARV as individual types of abuse rarely occur in isolation and HEART is designed to address ARV broadly. We will compare odds of reporting ARA at follow-up for the two arms by fitting a logistic regression model with any ARV at follow-up (yes or no) as the dependent variable, baseline ARA

(yes or no) as a covariate, and study arm as focal predictor. This approach should have higher statistical power than the Fisher's Exact Test used in the power analysis, making our sample size somewhat conservative. We will analyze secondary outcomes (ARA perpetration, ARA victimization, recognition of abusive behaviors, knowledge of ARA resources, self-efficacy to use harm reduction strategies, use of harm reduction strategies and resources) similarly. Factors potentially affecting intervention efficacy (e.g., sex, gender, race/ethnicity, recognition of behaviors as abusive, intention to engage in healthy relationship behaviors, adolescent change talk, MI fidelity [MI-consistent/-inconsistent behaviors], intervention intensity [number of intervention topics discussed]) will be considered as additional model predictors. We will summarize demographics and report baseline prevalence of any ARA and individual types of ARA. We will check for differences in demographics and baseline variables between the two arms, as well as for demographic differences between participants and refusals.

2.3 A sample size of 69 per arm provides 80.4% power to detect a between-arm difference, assuming control and intervention arm TVD rates of 0.55 and 0.30, respectively, at 3 months at follow-up (two-sided Fisher's Exact Test at alpha=0.05). We set a final sample as n=174 participants (n=87 each arm) to account for an estimated 20% loss to follow up, based on our previous work.

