2.0 Objectives*

2.1 Purpose, specific aims or objectives:

Our primary aim is to determine feasibility of Emergency Department Healthcare Education Assessment and Response for Teen Relationships (ED-HEART). We will conduct a randomized, controlled trial using mixed methodology to assess eight

feasibility constructs: acceptability, demand, implementation, practicality, adaptation, integration, expansion, and limited-efficacy testing.

Secondary aims are to:

- Examine Theory of Planned Behavior constructs that may impact ED-HEART efficacy.
- Conduct exploratory analysis of factors that may impact efficacy and implementation of ED-HEART.

2.2 Hypothesis to be tested/Exploratory study design:

Hypothesis 1.1: ED-HEART will be feasible as measured by data from adolescents and ED stakeholders.

Hypothesis 1.2: Adolescents receiving ED-HEART will report less ARA at three-month follow-up, compared to controls.

| | |
|------------------------------------------------------------------------------------------|------------------------------------------------------------------------------|
|  Children/Minors (under 7 years of age) |  CM Employees |
|  Children/Minors (7-17 years of age) |  CM Students/Residents/ Fellows |
|  Neonates (infants less than 30 days old) |  Economically or Educationally Disadvantaged Persons |
|  Neonates of Uncertain Viability (infants less than 30 days old) |  Prisoners |
|  Non-Viable Neonates (infants less than 30 days old) | |
|  Wards of the State | |
|  Fetuses | |
|  Pregnant Women | |
|  Adults with impaired decision-making capacity | |

Adolescents aged 14-17 years:

- Adolescent assent procedures will follow practices accepted by the Society for Adolescent Health and Medicine and current regulatory guidelines and align with those previously used for CM studies involving adolescents
- All adolescents will be encouraged to ask questions, provided necessary time to consider participation, and able to stop participation at any time, should they choose to do so.

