Study surveys were developed by the study team and based on extant literature. Surveys will be delivered via REDCap and completed on a

smart phone, desktop, or tablet computer. Surveys and their domains are listed below.

- Adolescents:
 - Baseline Survey (intervention, control arms): unique code questions,³⁹ demographics, ARA victimization and perpetration,^{35,40,41} recognition of abusive behaviors,^{35,41} self-efficacy,⁴² consequences of ARA, ARA resource knowledge/use,³⁵ readiness to engage in healthy relationship behaviors
 - Exit Survey (intervention arm only): fidelity, acceptability, self-efficacy,³⁵ use of POC resources, ARA disclosure
 - Follow-up Survey (intervention, control arms): unique code questions,³⁹ ARA victimization and perpetration,^{35,40,41} recognition of abusive behaviors,^{35,41} self-efficacy,³⁵ consequences of ARA, ARA resource knowledge/use

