## 6 Study Methods

### 6.1 General Study Design and Plan

The ED-HEART pilot has been designed as a randomized controlled trial comparing enhanced standard of care (control study arm) to the ED-HEART intervention. Individuals will be randomized in a 1:1 allocation.

Subjects will be identified from the ED tracking board and approached to see if they would like to participate in the study. Once pre-screening has occurred and consent/assent has been obtained, individuals will fill out a baseline survey. Those in the ED-HEART study arm will additionally be given the ED-HEART intervention and an exit survey. Each arm will receive a 6-week check in and a 12-week follow-up survey. All completed surveys will be completed confidentially and will not contain identifying information. We will use a unique, participant-created code to link study surveys over time. Those individuals that refused to be part of the study will be given the option to complete a refusal survey.

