## 8 General Analysis Considerations

### 8.1 Planned Analyses

Descriptive summaries will be made for the Bowen model's eight constructs regarding feasibility (primary outcome). Specifically, the measures defined in the table below will be summarized.

Assessment of Bowen Feasibility Constructs		
Construct	Definition	Assessment measures
Acceptability	To what extent is ED-HEART suitable?	Adolescent surveys, Health Educator field notes
Demand	To what extent is ED-HEART likely to be used?	Proportion of screened adolescents eligible; proportion of eligible adolescents enrolled; Health Educator field notes
Implementation	To what extent can ED-HEART be delivered as planned?	Fidelity assessment per adolescent survey, Health Educator field notes, audio recordings of intervention delivery
Practicality	What factors make delivery challenging or facilitate delivery?	Health Educator field notes
Adaptation	To what extent does ED-HEART perform in a new system?	Comparison with published outcomes in original setting 
Integration	To what extent can ED-HEART be integrated within existing system?	Health Educator field notes
Expansion	To what extent can the existing system be expanded to provide ED-HEART?	Health Educator field notes
Limited efficacy	Are ED-HEART outcomes promising?	Primary outcome: any ARA at 3-month follow up  , per adolescent survey

Acceptability ratings will be collapsed to dichotomous variables. ED-HEART will be deemed acceptable if the test of the proportion of very/fairly satisfactory ratings for adolescents, the health educator, and ED staff being at least 85%. We will compare ED length of stay between the two arms and calculate the mean/median number of interruptions per participant, with a list of reasons for interruption. For limited efficacy assessment, our primary outcome is any ARA as individual types of abuse rarely occur in isolation and HEART is designed to address ARA broadly. We will compare odds of reporting ARA at follow-up for the two arms by fitting a logistic regression model with any ARA victimization at follow-up (yes or no) as the dependent variable, baseline ARA (yes or no) as a covariate, and study arm as focal predictor. This approach should have higher statistical power than the Fisher's Exact Test used in the power analysis, making our sample size somewhat conservative.

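### The protocol counts failure to prove that ratings fall below 85% as proof of acceptability, and the matching SAP sentence is incomplete and states no pass result

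*Protocol*

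**What the plan says.** Feasibility is the primary aim, and Hypothesis 1.1 in Protocol Section 2.2 states that "ED-HEART will be feasible as measured by data from adolescents and ED stakeholders". Acceptability is one of the eight feasibility constructs, and the only one with a pass mark in the visible text.

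Protocol Section 27.0 reduces the ratings to two levels and applies a test to the share that are very or fairly satisfactory. The pass condition for adolescents, "the health educator, and ED staff being <85% is not statistically significant", is a non-significant result.

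The matching sentence in SAP Section 8.1 also begins with a test of the proportion, but runs on to "very/fairly satisfactory ratings for adolescents, the health educator, and ED staff being at least 85" per cent and stops. It has no verb after that, and it names no test result that would be a pass. SAP Section 9 records no change to the SAP, so nothing explains the difference.

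Neither document gives the test, alpha, sidedness or number of raters per group for this rule, or says whether the three groups are pooled. On sources, Protocol Section 9.0 lists "Exit Survey (intervention arm only): fidelity, acceptability", SAP Section 6.1 agrees ("Those in the ED-HEART study arm will additionally be given the ED-HEART intervention and an exit survey"), and the Acceptability row of Table 2 gives "Adolescent surveys, Health Educator field notes".

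**The concern.** A test for a rate below 85% starts from the assumption that the rate is 85% or better. A non-significant result means only that the data did not contradict that assumption. Using it as the pass condition turns lack of evidence into a positive finding, and the incentive runs the wrong way: a group with few ratings can hardly fail.

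The SAP does not repair this. An analyst cannot carry out its sentence as written and must choose between two readings. If it means an observed proportion of at least 85%, some results pass under one document and fail under the other. If it is a damaged copy of the protocol sentence, there is no conflict, but the inverted rule stands in both documents. Each reading needs a correction.

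At stake is the label itself. An intervention whose true satisfaction rate is below the plan's own target could be reported as acceptable on a construct of the primary aim.

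**Working it through.** **Inputs.** The target of 85% is from Protocol 27.0 and SAP 8.1. There are 87 participants per arm (Protocol 7.0 and 27.0), and only the ED-HEART arm completes the exit survey. The figure of 69 per arm is what the sample-size text requires, enlarged to 87 "to account for an estimated 20% loss to follow up".

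**Assumptions, which the documents do not fix.** One rating per adolescent; exact binomial test, one-sided 0.05; 69 to 87 completed exit surveys. The 20% loss is stated for follow-up, and no exit-survey completion rate is given, so 69 is only a plausible lower figure.

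**The plan's own figures.** No operating characteristic is given for the acceptability rule. The figures nearby reproduce: Fisher's exact power at 69 per arm for 0.55 against 0.30 is 0.804, and 69/(1 − 0.20) = 86.25, rounded up to 87. Nothing below depends on the power figure.

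**Step 1: lowest passing count under the protocol rule.** This is the smallest x with P(X ≤ x | n, 0.85) > 0.05. At n=87, P(X ≤ 67) = 0.031 (significant, fails) and P(X ≤ 68) = 0.056 (not significant, passes). The floor is 68/87 = 78.2%, with exact 95% CI 68.0% to 86.3%.

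**Step 2: lowest passing count if the observed proportion must reach 85%.** 0.85 × 87 = 73.95, so 74/87 (85.1%).

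**Step 3: chance of the acceptable label at n=87.** P(X ≥ 68) against P(X ≥ 74):

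| True rate | Protocol rule | Observed at least 85% |
|---|---|---|
| 70% | 5.8% | 0.1% |
| 75% | 29.4% | 1.7% |
| 80% | 71.9% | 14.7% |
| 85% | 96.9% | 56.7% |
| 88% | 99.7% | 84.4% |
| 90% | 99.97% | 95.0% |

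**Step 4: results on which the rules differ.** Counts of 68 to 73 of 87 pass the first rule and fail the second. P(68 ≤ X ≤ 73) is 57% at a true 80%, 40% at 85% and 5% at 90%.

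**Step 5: other numbers of raters.** For every n from 69 to 87 the protocol floor lies between 77.1% (54/70) and 78.8% (67/85). A true 80% passes 67% to 78% of the time under the protocol rule and 10% to 17% under the observed-proportion rule. Within this range the floor moves little and not steadily. It drops clearly only in small groups: 30/40 (75.0%) passes, and so does 14/20 (70.0%), where a true 80% is labelled acceptable 91% of the time.

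**Step 6: other alpha.** At one-sided 0.025 and n=87 the floor falls to 67/87 (77.0%), and a true 80% passes 80% of the time.

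**The case against.** The strongest reply is that this is a pilot. Both documents summarise feasibility descriptively, and no decision to proceed or stop is tied to the label. A lenient screen can be a deliberate choice: at n=87 it keeps an intervention truly at 85% about 97% of the time and stops one truly at 70% about 94% of the time (1 − 0.058). That limits the harm and rules out saying that anything would pass. It does not rescue the rule, because the plan chose a test and a two-way label and does not present the leniency as intended.

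Second, the 72% figure applies only if the protocol rule governs. If the SAP means the observed proportion, the analysis document already contains a sound threshold, and what is left is a broken sentence and a mismatch. This stands: the two harms are alternatives and do not add up. A reader might infer a definite contradiction between the documents, but the SAP sentence is too incomplete to establish one.

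Two further inferences go too far. One is that no ED staff ratings are collected. Protocol Section 25.0 begins "Sources of data include adolescent participants (surveys, audio recordings of ED-HEART delivery), the medical records of adolescent participants" and names no staff survey, and Table 2 names none for acceptability. But the text available here passes from the hypotheses in Section 2.2 straight to a population checklist, so a staff instrument may be described in sections not visible. This is a query only. The other is that the health educator, as a single rater, could never fail. One rating alone could not reach significance (0 of 1 gives p = 0.15), but the documents do not say that there is only one rating or that this group is tested alone; field notes could hold one per session.

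**Conclusion.** The point holds. The protocol rule is wrong as written, because it awards the label for a non-significant shortfall, and the SAP sentence cannot be carried out as it stands. Under the stated assumptions a true rate of 80% against an 85% target is labelled acceptable about 72% of the time at n=87 (67% to 78% for n=69 to 87), against 15% (10% to 17%) under an observed-proportion rule. The exact size depends on the test, alpha and number of raters, none of which the plan fixes. The direction of the fault does not.

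The consequence is a misleading feasibility label. A reader might infer a wrong decision about the trial or its successor, but the documents attach no such decision to the label. This should be fixed before analysis; it does not threaten the conduct of the trial.

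**What to change.** Put the same complete rule in Protocol 27.0 and SAP 8.1, and remove non-significance as a pass condition. For example: *A rater group finds ED-HEART acceptable if at least 85% of its observed ratings are very or fairly satisfactory. The proportion is reported with its exact 95% confidence interval. Rater groups are reported separately and not pooled.*

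The rule should also state:

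- whether the unit is the adolescent or the survey item, and how several items combine, since the protocol speaks of more than one two-level variable;
- that it applies to each group the documents name. If the sponsor wants adolescents alone to decide the label, it should record that as a deliberate change, because both documents now count all three groups;
- where the ED staff ratings come from, if this is not already set out in a section not visible here.

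**Cost.** The change to the rule is wording and needs no new adolescent data; if no staff instrument exists, staff ratings would need one. The rule is stricter. At n=87 a true 85% misses the label 43% of the time (1 − 0.567), against about 3% (1 − 0.969) under the protocol rule. For n=69 to 87 the miss rate runs from 42% (n=80) to 54% (n=73). A true 90% still passes 95% of the time at n=87. Because an intervention exactly at target misses about as often as it passes, the confidence interval must be read beside the label. A sponsor who prefers another threshold or a formal test can choose one, but must state it in full.
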